7. BENEFITS

The current standard of care in the management of CRS patients with and without nasal polyposis after endoscopic sinus surgery involves a non-standardized regimen of antibiotics and systemic steroids. However, the use of oral steroids in this period is based on anecdotal evidence and expert opinion (level IV evidence). Given the known risks of oral steroid use, it is important to definitively establish their utility and to investigate alternatives. Our study first seeks to more clearly define the role of steroids, both oral and topical, in the perioperative setting. Furthermore, we intend to establish topical steroids as a safer but equally effective therapy. This information will be invaluable to the field and practice of Rhinology. There is a great need for additional investigation to determine whether steroids truly have a beneficial role in post-operative CRS patients. We endeavor to provide randomized, controlled data on which clinicians may base their therapeutic decisions. In addition, the introduction of topical steroids into routine post-operative care would fundamentally change current clinical practices, and may even influence future guidelines. For patients, this may transform their post-operative care into one that is more easily tolerated with less detrimental effects on health.

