2. STUDY PROCEDURES

a. Procedures

Screening: Patients who have been recommended to undergo endoscopic sinus surgery by our department will be recruited for the study and informed of its purpose pre-operatively. SNOT22 scores (a quality of life survey well established in Rhinology) and Lund-Kennedy endoscopic exam scores (an quantitative clinical assessment of disease severity) will be recorded in their medical records. This is the same protocol performed for all patients seen in our clinic regardless of their enrollment in the study. Randomization and Treatment Groups: The patients that wish to participate will be randomized into two treatment arms by our nurse practitioner based on a random number generator. They will receive one of the following post-operative regimens: 1) oral steroid (treatment) + steroid spray (treatment) 2) oral placebo (control) + steroid spray (treatment) These medications will be manufactured and packaged by an independent compounding pharmacy, and prescribed by our nurse practitioner at the preoperative visit. Patients will begin their therapy on the first post-operative day. All oral steroid regimens will be given in our institution's standard 12 days taper, while topical steroids will be delivered via a metered dose nasal spray bottle for two weeks. All study patients will receive identical perioperative antibiotic therapy. We do not anticipate these medications to be an inconvenience to study patients as all proposed interventions are not different from routine post-operative care. In addition, patients undergoing surgery will have already trialed these medications as part of their pre-operative medical therapy. Surgery: Routine endoscopic sinus surgery will be performed per our institution's standard protocol. In this step there will be no difference in treatment from those patients not enrolled in the study. Post-Operative Care: At this point, patients will begin therapies according to the treatment arm to which they have been randomized. Study patients will attend post-operative appointments at identical time points to non-study patients. These will take place at the following intervals: Post-operative visit 1: 1-2 weeks Post-operative visit 2: 6-8 weeks Post-operative visit 3: 12-16 weeks Post-operative visit 4: 6 months Experimental therapy will finish after 2 weeks. At this visit, all patients will then be maintained on intranasal steroid spray and nasal saline irrigations, which is the commonly employed therapeutic standard. Thereafter, patients will, per standard protocol, be followed on an observational basis depending on the severity of symptoms and response to treatment. At each visit, as is done for all individuals, SNOT-22 and LundKennedy endoscopic exam scores will be repeated and recorded.

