
b. Procedure Risks

This study does not seek to evaluate a novel research procedure. Rather, we endeavor to determine if a procedure already in place nearly universally is, in fact, beneficial, as there is a

distinct lack of evidence of suggest so. Overall, we are investigating a procedural method that will have fewer side effects than the currently accepted practice.

c. Use of Deception in the Study

NA

d. Use of Audio and Video Recordings

NA

e. Alternative Procedures or Courses of Treatment

All reasonable alternatives are included as a treatment arm in this study. There is no standard of care that is being withheld from patients in any group.

f. Will it be possible to continue the more (most) appropriate therapy for the participant(s) after the conclusion of the study?

Yes, patients will stop all experimental therapies at the 2 week mark. They will then be placed on the typical post-operative regimen, which includes a nasal steroid spray and twice daily saline irrigations. They will continue to be followed in our clinic after the 4 week mark, and their therapies tailored to their current symptoms and the endoscopic appearance of the nasal cavity.

g. Study Endpoint(s)

Currently, our post-operative protocol dictates that patients will be seen in clinic at 1 week, 3 weeks, and 6 weeks after surgery. We will only slightly alter this timeline for study patients. At the 2 week appointment, all experimental therapies will be completed. Patients will then be started on intranasal steroid sprays and saline irrigations so as not to deviate for an extended period from currently accepted practices. We will use the final scheduled appointment at 4 weeks after surgery as the official end point for comparison of treatment arms. Additionally, outcomes evaluated will be the symptom questionnaire and the endoscopic exam score at each visit. If, during the course of follow up, one regimen proves to be clearly superior to another, the study will be terminated and patients will receive the optimal therapy. By power analysis, we require 50 patients to achieve statistical significance. If there is a clearly optimal therapy determined in these first 50 patients, we will end our research at that time. All patients will continue to be followed beyond 4 weeks depending on symptom severity and response to treatment

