support its use (1). Therefore, this almost universal current practice is perpetuated by anecdotal data and expert opinion. Furthermore, systemic steroids are associated with known significant side effects and potential drug interactions. These may be severe and include but are not limited to high blood pressure, hyperglycemia and diabetes, adrenal suppression, weight gain, glaucoma, osteoporosis, fluid retention, gastrointestinal bleeding, ulcers, and mood changes (2). Thus, oral steroids potentially pose a significant risk, have unproven benefit, and are not appropriate for repeated or longterm use – an unfortunate obstacle in treating a chronic disease. Recently, steroids dissolved in a saline irrigant have been increasingly used and proven to be effective in the routine management of CRS. Furthermore, several studies have suggested the utility and safe side effect profile of these medications; however, the data supporting their use as a perioperative treatment is distinctly lacking. While the data to support the utility of topical steroids in the treatment of CRS is evident, relatively few groups have explored topical steroid irrigations specifically as a peri-operative intervention. Fandino et al conducted a meta-analysis of 13 randomized clinical trails and cohort studies examining the use of topical steroids delivered via drops, sprays, nebulizers, or irrigations for patients with CRS with nasal polyps who had previously undergone endoscopic sinus surgery. According to his analysis, intra-nasal corticosteroids had a significant beneficial effect on symptom scores and a reduction in polyp scores. Additionally, the use of INCS decreased the rate of polyp recurrence, and did not alter adrenocorticotrophic hormones post-intervention, suggesting the intra-nasal delivery method to carry less risk than the oral version (3). Snidvongs et al conducted a study with 111 patients and reported significant improvement in symptom scores and endoscopy scores over those who did not receive postoperative topical steroids (4). Jang et al retrospectively evaluated 60 patients postsurgically who were treated with topical steroid deliveries and showed a significant decrease in quality of life and endoscopy scores after patients stopped their treatments (5). In summary, the data supporting the use of steroids in patients with CRS immediately after endoscopic sinus surgery is sparse. We, therefore, seek to more definitively elucidate the role and utility of steroid treatment in the peri-operative period. Furthermore, per our review of the literature, there has been no direct comparison of the traditional oral regimen to topical therapy (nasal spray). Could these be proven equally effective, topically delivered steroids may be considered as a replacement for systemic steroids. This would represent a significant shift and improvement in the current post-operative management of CRS. Patients would avoid the innumerable side effects of oral steroids, which are detailed above. Furthermore, while oral steroid usage is often limited by unwanted side effects, a topical regimen may be sustained over a prolonged period as a maintenance therapy if symptoms necessitate.

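### Both arms are assigned steroid spray, so the trial cannot deliver what section 7 claims about topical steroids; it tests only prednisone added to spray

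*Protocol*

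**What the plan says.** **The claim.** Protocol section 7 (Benefits) says: "Our study first seeks to more clearly define the role of steroids, both oral and topical, in the perioperative setting". The same paragraph goes on to say that topical steroids are to be established as a safer treatment that works equally well.

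**The background.** Section 3a remarks that "there has been no direct comparison of the traditional oral regimen to topical therapy (nasal spray" and adds, conditionally, that topical steroid might replace systemic steroid if the two were shown to be equally effective.

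**The arms.** Section 2a describes patients "randomized into two treatment arms by our nurse practitioner based on a random number generator". The arms are "1) oral steroid (treatment) + steroid spray (treatment") and "2) oral placebo (control) + steroid spray (treatment"). Treatment begins on the first post-operative day, and "topical steroids will be delivered via a metered dose nasal spray bottle for two weeks". After that, section 2a keeps all patients on spray with saline irrigation.

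**The stated aim and the analysis.** Section 1b asks only whether oral steroids have a peri-operative role. The SAP compares SNOT-22, Lund-Kennedy scores and adverse effects between the prednisone and placebo groups with t-tests at each time point.

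**The week-2 wording.** Section 2g, repeated in section 6e-iv, says of the time after experimental therapy ends: "Patients will then be started on intranasal steroid sprays and saline irrigations so as not to deviate for an extended period". Section 2f uses similar wording about placing patients on a regimen that includes nasal steroid spray.

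**The concern.** A randomised trial can estimate the effect only of something that differs between its arms. Here the oral component differs and the topical component does not. No arm lacks spray, and no arm receives prednisone without it. Section 7 nevertheless offers the trial as evidence on topical steroids and as support for their being equally effective.

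What is at stake is the conclusion. Suppose the arms turn out alike. That could mean that spray works and prednisone adds little, or that neither treatment does much and both groups recover from surgery at the same rate. The design cannot separate these. A reader relying on section 7 could take a null result as randomised proof that topical steroid is effective, and section 7 itself expects the work to influence practice and possibly guidelines.

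**Working it through.** **1. The plan's own figure.** Protocol section 2g and the SAP both say that a power analysis requires 50 patients. This cannot be reproduced, because no alpha, sidedness, power, effect size, SD or margin is given. As a back-solve only, assuming two-sided alpha 0.05, 80% power and 1:1 allocation, 50 in total corresponds to an effect of about 0.8 SD. The main point does not depend on this figure.

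**2. What the two arms identify.** Inputs are the arm definitions in section 2a. Let μ be the mean outcome with neither steroid, o the effect of oral steroid and t the effect of spray, taken as additive.

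| Arm | Intercept | Oral | Topical | Mean |
|---|---|---|---|---|
| 1 | 1 | 1 | 1 | μ + o + t |
| 2 | 1 | 0 | 1 | μ + t |

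- Arm 1 − arm 2 = o, so the oral effect given spray is estimable.
- μ and t appear only as the sum μ + t. Replacing (μ, t) by (μ + k, t − k) for any k leaves both arm means unchanged, so t is not estimable.
- o − t requires t, so the oral-versus-topical difference is not estimable.

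The design matrix has rank 2 with three unknowns. Adding the row for t, or for o − t, raises the rank to 3, which confirms that neither lies in the space the data can reach. Sample size does not enter.

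**3. Without additivity.** With an interaction γ, arm 1 has mean μ + o + t + γ and the difference is o + γ: the effect of prednisone in the presence of spray. The effect of prednisone alone is then not identified either.

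**4. What would change this.** As an illustration, adding a row (1, 1, 0), oral steroid with placebo spray, brings the rank to 3 and makes o, t and o − t all estimable under the additive model. That would be a different trial.

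**5. The question the contrast can address.** Whether prednisone may be omitted on top of spray is a comparison of the two randomised arms. Assuming 1:1 allocation, a true difference of zero, one-sided alpha 0.025 and n per arm, the smallest supportable margin in SD units is (1.960 + z_power) × √(2/n), with z_power 0.842 at 80% power and 1.282 at 90%.

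| Total | n per arm | 80% power | 90% power |
|---|---|---|---|
| 50 (power analysis) | 25 | 0.79 | 0.92 |
| 75 (SAP planned size) | 37.5 | 0.65 | 0.75 |
| 100 (upper end of the 80 to 100 in section 5a) | 50 | 0.56 | 0.65 |

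The same values are the detectable differences for a two-sided 0.05 test. Dropout is ignored.

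**6. When spray begins.** Section 2a makes spray part of both arms for the first two weeks and then has patients maintained on it. Sections 2g and 6e-iv have them started on it after week 2, and section 2f has them placed on it then. On either reading the arms do not differ in assigned spray, so steps 2 and 3 stand. What is left unclear is the background treatment in weeks 0 to 2.

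**The case against.** The strongest reply is that the stated objective and the analysis already agree. Section 1b is about oral steroids, the arms test oral steroids, and the SAP compares prednisone with placebo and makes no topical claim. On this view the fault is loose wording in a Benefits section. This largely stands: the add-on comparison is valid, and neither section 1b nor the SAP comparison is in error. But section 7 states what the study will establish and why it is worth doing, so the wording needs correcting.

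A second reply is that spray alone versus spray plus prednisone is in effect topical care versus traditional care. That is partly right. The contrast does address whether prednisone can be omitted, and for that question a margin and an interval would help. It still leaves open whether spray does anything.

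A reader might infer several stronger criticisms that the documents do not support:

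- *That section 3a promises an oral-versus-topical comparison.* It names a gap in the literature and adds a conditional; it does not list the comparison as an objective.
- *That the trial gives no randomised information on comparative safety.* The SAP compares adverse effects between spray alone and spray plus prednisone. Only the safety of spray itself, or of spray against oral steroid alone, is out of reach.
- *That topical exposure is identical throughout follow-up.* This holds for assigned treatment. Section 2f lets therapy be tailored after 4 weeks, so treatment received could diverge. Because that divergence is not randomised, it would not rescue a topical claim.
- *That the week-2 wording turns the contrast into oral steroid versus no steroid.* Only section 2a defines the arms, and the other sections can be read as describing the start of maintenance treatment.

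**Conclusion.** The topical claims in section 7 are wrong as written. With the arms of section 2a, randomised information on the effect of topical steroid, and on oral versus topical steroid, is zero at any sample size. This rests only on the assigned treatments and requires no assumption about effect size or variability.

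The trial's main comparison is not damaged. It estimates the effect of prednisone versus placebo on top of spray, as section 1b and the SAP intend. Finding no significant difference on the planned t-tests would not by itself make the regimens equally effective. Under the assumptions shown, the trial could support margins no tighter than about 0.79 SD with 50 patients or 0.65 SD with 75 at 80% power.

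The inconsistency about when spray begins is real but secondary.

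**What to change.** 1. **Section 7.** Replace the claims about topical steroids with: *the effect of adding a 12-day oral prednisone taper, versus placebo, to steroid nasal spray after sinus surgery*. This follows the arms as section 2a defines them.
2. **Section 3a.** Keep the literature gap as background, and add that this trial does not itself compare oral with topical steroid.
3. **Conclusions.** Apply the same limit when reporting. A null result may be described as bearing on whether prednisone adds to spray; it should not be described as evidence that spray works. If equal effectiveness of the two regimens is to be claimed, a margin and a confidence interval for the difference are needed. Since the SAP is written in the past tense, a margin chosen now should be labelled with when it was set.
4. **Reconcile** section 2a with sections 2f, 2g and 6e-iv, so that background treatment in weeks 0 to 2 is unambiguous, and keep the wording in item 1 consistent with the result.

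The cost is a few sentences: no added patients, visits or analyses for items 1, 2 and 4. The downside is a narrower claim. Section 1b and the SAP comparison need no change on this account.

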1. PURPOSE OF THE STUDY

a. Brief Summary

After patients with chronic rhinosinusitis (CRS) undergo sinus surgery, they are typically instructed to take oral steroids for several days to weeks. However, there is limited data to suggest this is a beneficial practice, and oral steroids have been shown to have significant and unpleasant side effects. This study will investigate whether there is truly evidence based utility to the use of steroids after sinus surgery

b. Objectives

Chronic rhinosinusitis is a disease that affects an estimated 13% of the adult population. Patients with this disease suffer from reduced quality of life, impaired sleep, fatigue, acute infections, and chronic pain. Healthcare expenditures for CRS are estimated at \$8.6 billion annually, with the majority of costs arising from repetitive physician visits, emergency department encounters, and medications. Despite its prevalence, relatively little is understood about optimal medical therapy in the post-operative period. As described above, oral steroids are routinely prescribed after sinus surgery based on anecdotal data and expert opinion rather than convincing, randomized controlled data. The aim of conducting this study, therefore, is to determine if oral steroids have a role in the peri-operative treatment of patients with CRS. This study would contribute a wealth of important data to the field of Rhinology and the management of CRS. The role of steroids in the peri-operative period would be further elucidated, providing randomized controlled data with which providers may make informed therapeutic decisions. In summary, the results of this study have significant potential to influence current practice and management guidelines.

c. Rationale for Research in Humans

The purpose of the study is to test the efficacy of of a medication in individuals with CRS, which is not a disease known to be accurately duplicated in any other model.

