6. RISKS

a. Potential Risks

i. Investigational devices

NA

ii. Investigational drugs

NA

iii. Commercially available drugs, biologics, reagents or chemicals

Oral Prednisone: The side effects of short courses of systemic steroids (<3 weeks) include stomach upset, weight gain, insomnia, hyperglycemia, hypokalemia, adrenal suppression, and mood changes. These can occur in up to 16% of patients, with stomach upset being the most common. These effects are all reversible after stopping the steroid. Topical Fluticasone: The side effects of topical steroids include dry throat, sore throat, nasal irritation, headache, nose bleeds. These are the more common side effects, the incidence of which is unknown. Rare and serious side effects include difficulty breathing, flu symptoms, and vision changes. Again, these typically improve after stopping the steroids. On very rare occasion, vision symptoms may be permanent. None of these interventions differ from those already being instituted by our staff.

iv. Procedures

See the risks of the commercially available drugs - None of these interventions differ from those already being instituted by our staff.

v. Radioisotopes/radiation-producing machines

NA

vi. Physical well-being

NA

vii. Psychological well-being

NA

viii. Economic well-being

NA

ix. Social well-being

NA

x. Overall evaluation of risk

Low - innocuous procedures such as phlebotomy, urine or stool collection, no therapeutic agent, or safe therapeutic agent such as the use of an FDA approved drug or device.

b. International Research Risk Procedures

NA

c. Procedures to Minimize Risk

Medication administration will be monitored during the post-operative visits. Patients will begin their assigned therapy the day after surgery, and then will be seen 1, 2, and 4 weeks post-operatively. Any side effects being encountered will be discussed at these visits, and specialty services available in a timely manner to address them if needed. Furthermore, patients have 24 hour access to a physician in the department, and are, at any time, able to call with questions or concerns regarding their treatment.

Identifiable patient information will be handled per institutional protocol. Unique login information is required for all persons wishing to access the electronic medical system. All communications with patient data are sent on a secured machine via an encrypted service that is password protected.

d. Study Conclusion

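### The protocol intends to show topical steroids equally effective, but the SAP only tests for differences and sets no margin or confidence-interval rule

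*Protocol*

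**What the plan says.** Section 1b (Objectives) sets a difference question: the aim "is to determine if oral steroids have a role in the peri-operative treatment of patients with CRS". Two other sections go further. Section 7 (Benefits) states that "we intend to establish topical steroids as a safer but equally effective therapy", and just before that says "Our study first seeks to more clearly define the role of steroids, both oral and topical, in the perioperative setting". Section 3a (Background) gives the practical consequence, in conditional form: "Could these be proven equally effective, topically delivered steroids may be considered as a replacement for systemic steroids".

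Section 2a defines two arms: oral steroid plus steroid spray, and oral placebo plus steroid spray.

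The SAP compares SNOT-22 total, SNOT-22 subdomains, Lund-Kennedy scores and adverse effects between prednisone and placebo by t-test at each time point. It gives a planned size of 75 and says that 50 were needed for statistical significance. Protocol Section 5a expects 80 to 100 to enrol. The decision wording in Sections 2g, 6d and 6e(iv) concerns stopping if one regimen is superior or optimal. Neither document contains a margin, an equivalence or non-inferiority hypothesis, or a confidence-interval rule.

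**The concern.** To conclude that two regimens are equally effective, or that one is not worse, the data must exclude a difference large enough to matter. A test whose null hypothesis is no difference does not do this, because failing to reject it may only reflect a small sample. As written, a non-significant t-test is the only result the plan offers towards the Section 7 intention, and it is not valid evidence for it.

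The arms impose a second limit. With spray in both, the contrast is prednisone added to spray against spray alone. It can address whether spray without prednisone is not worse. It cannot estimate the spray's own effect or compare topical alone with oral alone, so it cannot define the role of topical steroids in the way Section 7 says.

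At stake is the reading of a null result. It could be reported as support for replacing oral steroids while the data still allow a moderate prednisone benefit.

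**Working it through.** **Inputs from the documents.** Total N of 50 and 75 (SAP) and 100 (upper enrolment figure, Section 5a); two arms (Section 2a); unadjusted t-tests (SAP).

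**Assumed, because neither document states them.** 1:1 allocation, two-sided alpha 0.05, no dropout, and effects in SD units of 0.3, 0.5 and 0.8.

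**The plan's own figure.** N = 50 cannot be reproduced uniquely, since no alpha, power, effect or SD is given. One set that yields it is an effect of 0.8 SD with 80% power and two-sided 0.05. By the normal approximation, n per arm = 2 × (1.960 + 0.842)² / 0.8² = 24.5, rounded up to 25, or 50 in total. Nearby sets, such as 0.9 SD with 90% power, give 52. If this is the basis, the trial was sized for a large difference.

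**Precision.** Half-width of the 95% CI = t(0.975, N−2) × √(1/n1 + 1/n2), in SD units:
- N = 50: 2.011 × √(1/25 + 1/25) = 0.57
- N = 75: 1.993 × √(1/37 + 1/38) = 0.46
- N = 100: 1.984 × √(1/50 + 1/50) = 0.40

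**Chance that a true prednisone benefit d is non-significant.** This is 1 minus the noncentral-t power, with noncentrality d × √(n1·n2/N). For d = 0.5 the noncentrality is 1.77, 2.17 and 2.50 at the three sizes.

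| True benefit | N = 50 | N = 75 | N = 100 |
|---|---|---|---|
| 0.3 SD | 82% | 75% | 68% |
| 0.5 SD | 59% | 43% | 30% |
| 0.8 SD | 21% | 7% | 2% |

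The effect detectable with 80% power is 0.81, 0.66 and 0.57 SD respectively.

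**What a margin rule would deliver.** Suppose there is no true difference and a not-worse claim requires the 95% CI to exclude a disadvantage of spray alone as large as the margin. The chance of success is:

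| Margin | N = 50 | N = 75 | N = 100 | Total N for 80% |
|---|---|---|---|---|
| 0.3 SD | 18% | 25% | 32% | 351 |
| 0.5 SD | 41% | 57% | 70% | 128 |
| 0.8 SD | 79% | 93% | 98% | 52 |

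Apart from a negligible opposite tail, these percentages are the complements of the first table and are not separate evidence. They are repeated because they give the cost of adopting a margin. In simulation (200,000 trials per case), with a true benefit equal to the margin, the rule wrongly claims not worse in 2.5% to 2.6% of trials.

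**Comparison visit.** Any rule needs one visit, and the documents disagree. Section 2g says "We will use the final scheduled appointment at 4 weeks after surgery as the official end point for comparison of treatment arms", and Section 6e(iv) repeats this. Section 6c says patients "then will be seen 1, 2, and 4 weeks post-operatively". The SAP lists 1 week, 1 month, 3 months and 6 months. Section 2a begins "Post-operative visit 1: 1-2 weeks Post-operative visit 2: 6-8 weeks", continues with 12–16 weeks and 6 months, and has no visit at 4 weeks.

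**The case against.** The strongest reply is that equal efficacy is not a stated objective. The sentence is in the Benefits section, the Background version is conditional, and the objective in Section 1b matches the arms and the t-tests. The SAP itself claims neither equality nor replacement, and no passage says that p > 0.05 will be read as equality. All of that is true, and it limits the point to one added claim. It does not remove it: Section 7 states an intention of this study, and the plan contains no valid route to it.

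A second reply is that the SAP, dated July 2020, is in the past tense, so rewording the protocol may change little. That has some force. Reporting a CI and not calling a null result equality remain useful whatever the stage of the trial.

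Third, the margin figures assume an unadjusted comparison, although a preoperative baseline is collected. Baseline adjustment would help. For a 0.5 SD margin and assumed baseline correlations of 0.3, 0.5 and 0.7, the total N for an 80% chance falls from 128 to about 117, 97 and 67. At N = 75 the chance rises from 57% to about 61%, 69% and 85%. The unadjusted figures match the t-tests the SAP specifies, but the feasibility of a margin should be read with this qualification.

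Finally, the visit conflict is a separate inconsistency. It matters here only because a decision rule must name a visit, and it adds nothing to the severity of this point.

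**Conclusion.** The concern holds and should be fixed. The Section 7 intention cannot be met by difference tests without a margin, and the arms cannot support its wider wording on topical steroids. The formal objective is unaffected.

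The logical point needs no numbers. Its practical size depends on the assumptions listed above. For small to moderate benefits (0.3 to 0.5 SD), the chance of a misleading null result is 43% to 75% at the planned 75 patients. For a large benefit (0.8 SD) it is 7% at 75 patients and 2% at 100. These are illustrations in SD units and cannot be converted to SNOT-22 or Lund-Kennedy points from the documents.

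**What to change.** **In all cases (SAP).** Report the between-arm difference with a 95% CI, and state that a non-significant result will not be interpreted as equal efficacy.

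**Then choose one option.**

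- **A. Narrow the claim (sufficient on its own).** Reword Sections 3a and 7 to refer to prednisone added to steroid spray versus spray alone. Limit the statement about oral and topical steroids to whether spray suffices without prednisone. Cost: wording changes and one CI.
- **B. Keep a not-worse claim.** Before unblinding, name one primary outcome (SNOT-22 total or Lund-Kennedy), one comparison visit and one justified margin in that outcome's own units. If the data are already unblinded, label the margin post hoc. Claim not worse only if the CI excludes a disadvantage of spray alone as large as the margin; otherwise call the result inconclusive. Cost: justifying the margin, and accepting that a null result may be inconclusive. With unadjusted t-tests, the planned 75 patients suit only a wide margin; baseline adjustment could ease this.

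Neither option needs a new arm. Before a visit is named for Option B, reconcile the schedules in Sections 2a, 2g, 6c and 6e(iv) and the SAP. The SAP's 1-month collection suggests that a visit near 4 weeks took place, but Section 2a does not list one.
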